5.3 Safety assessment

Safety will be assessed by recording the nature and incidence of adverse events and serious adverse events. Adverse events will be assessed by direct questioning. An adverse event is defined as any unfavorable, unintended sign, symptom, syndrome or disease that develops or worsens with the use of a medicinal product, regardless of whether it is related to the medicinal product. All adverse events must be recorded on the case report form.

A serious adverse event is defined as any untoward medical occurrence that at any dose:

- results in death, is life threatening;
- requires hospitalization or prolongation of hospitalization;
- results in a persistent or significant disability or incapacity; or

- is a congenital anomaly or birth defect.

‘Life-threatening’ means that the person was at immediate risk for death; it does not refer to a adverse event that might have caused death if it were more severe. ‘Persistent or significant disability or incapacity’ means that a person’s ability to carry out normal life functions is substantially disrupted.

All serious adverse events occurring during the study must be recorded and reported by the principal investigator to the sponsor, regardless of whether the principal investigator considers the events to be related to the investigated medicine.

The investigator will collect information on any women who become pregnant while participating in this study and will record the information on the appropriate form. The pregnant woman will also be followed to determine the outcome of the pregnancy. Generally, follow-up will be no longer than 6–8 weeks after the estimated delivery date. Any premature termination of pregnancy will be reported. While pregnancy itself is not considered an adverse event or a serious adverse event, any complication of pregnancy or elective termination for medical reasons will be recorded as an adverse event or a serious adverse event. A spontaneous abortion is always considered a serious adverse event and will be reported as such.

6. STUDY ASSESSMENT

6.1 Screening and enrolment

All patients who meet the basic enrolment criteria (age, fever or history of fever if appropriate, symptoms of malaria, absence of danger signs in children in relation to malaria—child unable to drink or breastfeed, vomiting everything, recent history of convulsions, lethargic or unconscious state, unable to sit or stand, difficulty in breathing—, absence of signs of severe malaria, absence of severe malnutrition, pregnancy) during screening will be assigned a consecutive number and evaluated in greater depth by clinical staff. In children, care will be taken to detect early signs of febrile diseases other than malaria, as their presence will necessitate exclusion from the evaluation. The most frequent confounding condition is a lower respiratory tract infection: cough or difficult breathing, together with fast breathing, is an indicator for exclusion. Fast breathing is defined as a respiratory frequency $> 50/\text{min}$ in infants under 12 months of age and $> 40/\text{min}$ in children aged 12–59 months. Other relatively common febrile conditions are otitis media, tonsillitis, measles and abscesses. Patients with these conditions will not be enrolled but should be treated for both malaria (if they have parasitaemia) and the other infection, as appropriate.

The screening record form (Appendix 5) will be used to record the general information and the clinical observations on each patient being screened. If the patient meets the clinical criteria, he or she will be examined for parasitaemia. Once the patient meets all the enrolment criteria, he or she (if adults are included) or a parent or guardian in case of children will be asked for consent to participate in the study. Children from 12 years of age will also need to provide their assent to participate.

6.2 Follow-up

Patients who meet all the enrolment criteria will be given a personal identification number and will receive treatment only after the study has been fully explained to them and they have willingly provided informed consent. Any person who decides not to participate in the study will be examined, treated and followed-up by the health facility staff according to the standard of care established by the Ministry of Health.

The basic follow-up schedule is summarized in Appendix 6. A case report form (Appendix 7) and a serious adverse event report form (Appendix 8) will be used to record the general information and clinical observations on each patient enrolled into the study. The appointment schedule will be clearly explained, and a follow-up card with a personal identification number will be provided. House visits will be made in the event patient cannot make it to the clinic. If this is the case provide detail about the visiting staff and the study procedures that will be done at home. The health staff will send to the patient's residence and provides a transportation support for bringing the patient to the study site where he or she will receive the physical examination and laboratory test if necessary.

The day a patient is enrolled and receives the first dose of medicine is designated 'day 0'. All antimalarial treatment will be given by a study team member under supervision. Enrolled patients will be observed for at least 30 min after treatment to ensure that they do not vomit the medicine. If vomiting occurs within 30 min of treatment, the full treatment dose will be repeated. Ancillary treatment, such as antipyretics, will be provided if necessary to patients by the study team and documented on the case report form. Patients with persistent vomiting (i.e. necessitating more than a single repeat dose) will be excluded from the study and immediately referred to the health facility staff for appropriate management.

Thereafter, patients are required to undergo regular clinical reassessment. Blood films for parasite counts will be made on days 2, 3 and 7 and then weekly for the remainder of the follow-up period, i.e. on days 14, 21, 28, 35 and 42. Patients will be advised to return on any day during the follow-up period if symptoms return and not to wait for the next scheduled visit day. In particular, parents or guardians should be instructed to bring children to the centre at any time if they show any sign of danger (unable to drink or breastfeed, vomiting everything, presenting with convulsions, lethargic or unconscious, unable to sit or stand, presenting with difficult breathing), if they are still sick or if there is any cause for worry. Clinical reassessment will be sufficiently thorough to ensure patient safety and will include assessment not only for potential treatment failure but also for potential adverse reactions to the medicine. Additionally, blood films will be obtained whenever parasitological reassessment is requested by the clinical staff.

Because many medicines have to be given over several days, the initial visits are critical not only for assessing efficacy but also for ensuring patient safety; defaulters at this stage will not have received a complete course of treatment and may be at risk for clinical deterioration. All reasonable efforts will be made to find defaulters to ensure complete treatment. Similarly, the ultimate success of the study rests on minimizing loss to follow-up. While patients are encouraged to return on their own for scheduled follow-up visits, it is essential that provisions be made ahead of time for locating patients at home if they do not attend as requested. This requires obtaining detailed directions to the home during enrolment, and study team members familiar with the community will be responsible for home visits and means of transport for the patients. The schedule of treatment and follow-up examinations given in this protocol must be followed to ensure data integrity. Patients who fail to return on days 1 and 2 and miss one dose of the treatment will be withdrawn from the study definitively. After day 3, patients who fail to return on day 7 but are present on day 6 or 8 (likewise days 13/15, days 20/22, days 27/29, days 34/36 and days 41/43) may still be included in the analysis. Deviation from the protocol of more than 1 day should, however, be avoided (see also section 3.7).

7. DATA MANAGEMENT

The principal investigator will ensure that the study protocol is strictly adhered to and that all data are collected and recorded correctly on the case report form. Laboratory and clinical data will be recorded on a daily basis on the case report form designed for the study. Data derived

from source documents should be consistent with the source documents, or the discrepancies should be explained. Any change or correction to a case report form should be dated and explained and should not obscure the original entry. All case report forms will be checked for completeness.

After the study has been completed, data will be entered into a database by double independent data entry, according to WHO standard procedures.⁵ The study data will be stored in a computer database, maintaining confidentiality.

The principal investigator is responsible for keeping all screening forms, the case report form and the completed subject identification code list in a secure location. These documents will be destroyed immediately after the analyses have been completed. The sponsor will provide instructions to the principal investigator regarding destruction procedures of documents collected during the study.

8. STATISTICAL METHODS

8.1 Minimum sample size

As the treatment failure rate to ASMQ or ASP in the area is 10%, 10% has been chosen. At a confidence level of 95% and a precision around the estimate of 8%, a minimum of 54 patients must be included. With a 10% increase to allow loss to follow-up and withdrawals during the 42-day follow-up period, 60 patients should be included in the study per site for *P. falciparum* and 60 *P. vivax* and per species.

8.2 Analysis of data

Standard WHO spreadsheet will be used for data management and analysis. Data will be analysed by two methods: the Kaplan-Meier method and per-protocol analysis. In addition to the reasons for withdrawal listed in section 3.8, patients will be considered withdrawn from the analysis if the PCR results are unclassifiable or if the results of PCR indicate that the failure is due to reinfection with *P. falciparum*.

The final analysis will include:

- a description of all patients screened and the distribution of reasons for non-inclusion in the study;
- a description of all the patients included in the study;
- the proportion of adverse events and serious adverse events in all the patients included in the study;
- the proportion of patients lost to follow-up or withdrawn, with 95% confidence intervals and a list of reasons for withdrawal;
- the cumulative incidence of success and failure rates at day 28 and 42, PCR-uncorrected and PCR-corrected; and
- the proportion of early treatment failure, late clinical failure, late parasitological failure and adequate clinical and parasitological response at day 28 and 42, with 95%

⁵ WHO/GMP. *Standardized data entry for therapeutic efficacy tests*. Geneva, World Health Organization (<http://www.who.int/malaria/resistance>).

confidence intervals, PCR-uncorrected and PCR-corrected.

Guidelines on calculating the cumulative success or failure rate, the proportion of adequate clinical and parasitological response and treatment failure are given in Appendix 9.

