3.8 Patient discontinuation or protocol violation

Study patients who meet any of the following criteria will be classified as withdrawn.

- withdrawal of consent. A patient may withdraw consent at any time, without prejudice for further follow-up or treatment at the study site.
- failure to complete treatment, due to:
 - persistent vomiting of the treatment. A patient who vomits the study medication twice will be withdrawn from the study and given rescue treatment.
 - failure to attend the scheduled visits during the first 3 days; or
 - serious adverse events necessitating termination of treatment before the full course is completed. A patient can be discontinued from the study if the principal investigator decides so due to an adverse event of adequate nature or intensity. In this case, information on the adverse event and symptomatic treatment given must be recorded on a case report form. If the adverse event is serious, the principal investigator must notify the sponsor or its designee immediately and follow the reporting procedures described in section 5.3.
- enrolment violation:
 - severe malaria on day 0; or
 - erroneous inclusion of a patient who does not meet the inclusion criteria.
- voluntary protocol violation: self- or third-party administration of antimalarial drug (or antibiotics with antimalarial activity) (Appendix 2);
- involuntary protocol violation:
 - occurrence during follow-up of concomitant disease that would interfere with a clear classification of the treatment outcome;
 - detection of mono-infection with another malaria species during follow-up; or
 - misclassification of a patient due to a laboratory error (parasitaemia), leading to administration of rescue treatment.

Patients who are withdrawn will nevertheless be followed up until recovery or the end of follow-up, if possible; however, no treatment outcome will be assigned to these patients, and they will be censored or excluded from the analysis. The reasons for discontinuation or protocol violation will be recorded on the case report form.

Pregnancy detected during the course of follow-up does not constitute a reason for withdrawal but the event must be recorded and managed as described in section 5.3.

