APPENDIX 8. GUIDELINES FOR ANALYSIS OF RESULTS

End-point for day X (X = 28 or 42)	PCR-uncorrected results	
	Cumulative success or failure rate (Kaplan-Meier analysis)	Proportion (per-protocol analysis)
Adequate clinical and parasitological response on day X	Success	Success
Early treatment failure	Failure	Failure
Late clinical failure before day 7	Failure	Failure
Late clinical failure or late parasitological failure on or after day 7	Failure	Failure
Other species infection	Censored day of infection	Excluded from analysis
Lost to follow-up	Censored last day of follow-up according to timetable	Excluded from analysis
Withdrawal and protocol violation	Censored last day of follow-up according to timetable before withdrawal or protocol violation	Excluded from analysis

End-point for day X (X = 28 or 42)	PCR-corrected results	
	Cumulative success or failure rate (Kaplan-Meier analysis)	Proportion (per-protocol analysis)
Adequate clinical and parasitological response at day X	Success	Success
Early treatment failure	Failure	Failure
Late clinical failure before day 7	Failure	Failure
Late clinical failure or late parasitological failure on or after day 7		

 • falciparum recrudescence* 	Failure	Failure

 • falciparum reinfection* 	Censored day of reinfection	Excluded from analysis

 • other species mixed with falciparum recrudescence 	Failure	Failure

 • other species mixed with falciparum reinfection 	Censored day of reinfection	Excluded from analysis

 • other species infection 	Censored day of infection	Excluded from analysis

 • undetermined or missing PCR 	Excluded from analysis	Excluded from analysis
Lost to follow-up	Censored last day of follow-up according to timetable	Excluded from analysis
Withdrawal and protocol violation	Censored last day of follow-up according to timetable before protocol violation or withdrawal	Excluded from analysis

* WHO. *Methods and techniques for clinical trials on antimalarial drug efficacy: genotyping to identify parasite populations*. Geneva, World Health Organization, 2008 (<http://www.who.int/malaria/resistance>)

NOTE:

COMBINED SITE

HC

COMBINDED HC

TRAPEANG CHO

ORAL

VEUNSAI

KACHUON HC & VIRAKCHEY

KEO SEIMA

SEN MONOROM

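### Section 8.2 withdraws PCR-confirmed reinfections and unclassifiable PCR results without limiting this to the PCR-corrected analysis, contradicting the PCR-uncorrected guideline table

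*Protocol*

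**What the plan says.** Protocol section 8.2 opens with the methods: "Data will be analysed by two methods: the Kaplan-Meier method and per-protocol analysis". It then extends the withdrawal reasons of section 3.8 by two PCR-based grounds. One concerns genotyping that gives no answer: "patients will be considered withdrawn from the analysis if the PCR results are unclassifiable". The other concerns new infections, with withdrawal "if the results of PCR indicate that the failure is due to reinfection with *P. falciparum". Nothing ties this rule to one of the two sets of results.

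Section 3.8 says what withdrawal means: "no treatment outcome will be assigned to these patients, and they will be censored or excluded from the analysis".

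Section 8.2 goes on to promise "the cumulative incidence of success and failure rates at day 28 and 42, PCR-uncorrected and PCR-corrected", and asks for the outcome proportions in both forms as well. For the calculation rules it sends the reader elsewhere: "the proportion of adequate clinical and parasitological response and treatment failure are given in Appendix 9". The tables that give these rules are headed Appendix 8, a number that the serious adverse event form also carries.

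In those tables:

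- PCR-uncorrected: "Late clinical failure or late parasitological failure on or after day 7 Failure Failure", that is, a failure under both methods with no split by PCR result.
- PCR-corrected: a falciparum reinfection is "Censored day of reinfection" for Kaplan-Meier and excluded for per-protocol. Undetermined or missing PCR is excluded under both methods.
- Both tables have a separate row for withdrawal: censored at the last scheduled visit beforehand (Kaplan-Meier), or excluded (per-protocol).

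**The concern.** A P. falciparum patient whose parasites return on day 28 and whose PCR shows a new infection is a failure under the PCR-uncorrected table. Under section 8.2 the same patient is withdrawn, and the withdrawal row of that same table censors or excludes them. An unclassifiable PCR result meets the same conflict. The protocol states both rules and does not say which governs, so this is a contradiction and not a detail left to an analysis plan.

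At stake is the PCR-uncorrected failure rate. It is the one P. falciparum efficacy result that should not depend on genotyping, and it shows how many treated patients had parasites again by day 28 or 42. If PCR decides who enters it, it loses that meaning and is biased low. The results are meant to inform national treatment policy.

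**Working it through.** **Inputs from the protocol.** Section 8.1 gives a 10% failure rate, 95% confidence, 8% precision, a minimum of 54 patients, and 60 after allowance for losses. These figures reproduce: n = 1.96² × 0.10 × 0.90 / 0.08² = 54.02, and 54 / 0.90 = 60. They are not in dispute.

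**Assumed inputs.** The protocol gives no number of reinfections or unclassifiable PCR results, so these are varied. Five recrudescences among 54 (9.3%) stand for the 10%. That is a second assumption, because section 8.1 does not say whether its 10% is PCR-corrected.

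**Per-protocol.** Let k be the number of reinfections, with no unclassifiable PCR.

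- PCR-uncorrected by the table: (5 + k) / 54
- PCR-uncorrected with section 8.2 applied: 5 / (54 − k)
- PCR-corrected by the table: 5 / (54 − k), identical to the line above

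| k | Uncorrected, by table | Uncorrected, under 8.2 (equals corrected) | Difference (points) |
|---|---|---|---|
| 0 | 5/54 = 9.3% | 5/54 = 9.3% | 0 |
| 1 | 6/54 = 11.1% | 5/53 = 9.4% | 1.7 |
| 2 | 7/54 = 13.0% | 5/52 = 9.6% | 3.3 |
| 3 | 8/54 = 14.8% | 5/51 = 9.8% | 5.0 |
| 5 | 10/54 = 18.5% | 5/49 = 10.2% | 8.3 |

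At k = 3 the exact 95% interval is 6.6% to 27.1% by the table and 3.3% to 21.4% under 8.2.

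**Unclassifiable PCR.** With 5 recrudescences, no reinfections and 2 unclassifiable results, the table gives 7/54 = 13.0% and section 8.2 gives 5/52 = 9.6%. With 3 reinfections as well, the figures are 10/54 = 18.5% and 5/49 = 10.2%.

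**Kaplan-Meier at day 42.** Take recrudescences on days 21, 28, 28, 35 and 42, reinfections on days 28, 35 and 42, and 46 patients free of parasites to day 42.

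- Uncorrected by the table: 8/54 = 14.8%.
- Under 8.2, censored at the previous scheduled visit: 1 − (53/54)(50/52)(48/49)(46/47) = 9.5%.
- Under 8.2, excluded: 5/51 = 9.8%.
- Corrected by the table, censored on the day of reinfection: 1 − (53/54)(51/53)(49/50)(47/48) = 9.4%.

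For Kaplan-Meier the agreement with the corrected rate is therefore close but not exact. Over a grid of 3 or 5 recrudescences, 0 to 8 reinfections and 0 or 2 unclassifiable results, the Kaplan-Meier rate under 8.2 stayed within about 1.1 points of the corrected rate.

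**The case against.** The best defence is that the document as a whole shows what was meant. Section 8.2 asks for both sets of results, which would be largely pointless if its own sentence made them nearly the same. The uncorrected table has a specific row for late failures, and a specific row would normally prevail over a general withdrawal sentence. Section 3.8 does not list reinfection among its reasons. The final-day case report form in Appendix 7 records the outcome, the PCR result and the PCR-corrected result in three separate blocks, and the failure criteria in Appendix 4 do not mention PCR.

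This defence carries weight. It makes a corrected-only intent likely, and it means that no data are lost: the uncorrected outcome can be recovered under either reading. It does not remove the contradiction. Section 8.2 states its rule for the analysis without limit, nothing says that the tables prevail, and the pointer to them gives the wrong appendix number.

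Two stronger readings are tempting and are not supported. A reader might infer that the PCR-corrected Kaplan-Meier result is also compromised, because withdrawal censors at the previous visit while the table censors on the day of reinfection. In the example this moves the estimate by about 0.1 point (9.5% against 9.4%), which is immaterial. A reader might also extend the problem to P. vivax, but section 3.1 restricts the PCR distinction to P. falciparum patients.

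**Conclusion.** The contradiction stands as a wording fault with a real consequence if section 8.2 is followed literally. For P. falciparum, the per-protocol PCR-uncorrected failure rate then equals the corrected rate exactly, the Kaplan-Meier rate nearly equals it, and both are biased low. The illustrative understatement is 1.7 to 8.3 percentage points for 1 to 5 reinfections among 54 patients, against a planned precision of 8 points.

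That size rests on assumed counts and on reading the 10% as recrudescence. It is zero if there are no reinfections and no unclassifiable PCR results. A reader might infer that the sponsor intends to report a PCR-filtered rate as uncorrected. The tables and the case report form point the other way, so the point is that the text permits this error, not that it is planned.

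**What to change.** In section 8.2, keep the section 3.8 withdrawal reasons for both sets of results and replace the PCR part of the sentence with wording such as:

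> For the PCR-corrected results only, late failures on or after day 7 due to P. falciparum reinfection are censored on the day of reinfection (Kaplan-Meier) or excluded (per-protocol), and those with undetermined or missing PCR are excluded. In the PCR-uncorrected results all such P. falciparum failures count as failures whatever the PCR result.

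State that the guideline tables govern if the text and the tables differ. Give those tables an appendix number of their own and make the reference in section 8.2 match it.

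The cost is a short change of wording and a corrected cross-reference, agreed under section 8.4. Data collection, procedures and the sample size of 54, raised to 60, stay as they are.
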